2.3 Treatment comparisons

Eligible individuals who have provided and consent will be allocated to tecovirimat or placebo using a minimised randomisation program that helps maximise balance between the allocated treatment groups with respect to important prognostic variables (including age [<18 , ≥ 18 - <40 , ≥ 40], sex at birth [male/female], previous orthopoxvirus vaccination [yes/no/not known], severity [localised vs disseminated rash (defined as >1 area, e.g. groin & head)], and days since lesion onset [≤ 7 days or >7 days]).

Randomised participants will be issued with a supply of tecovirimat capsules (200mg) or placebo capsules to be taken orally with food as follows:

- Adults aged 18 years or older: three capsules twice a day for 14 days (total daily tecovirimat dose: 1200 mg)
- Children and adolescents aged <18 years:
 - Estimated body weight ≥ 13 to <25 kg: one capsule twice a day for 14 days (total daily tecovirimat dose: 400 mg).
 - Estimated body weight ≥ 25 to <40 kg: two capsules twice a day for 14 days (total daily tecovirimat dose: 800 mg).
 - Estimated body weight ≥ 40 kg: three capsules twice a day for 14 days (total daily tecovirimat dose: 1200 mg).

Although PK/PD modelling suggest that higher doses may be preferable in adult patients weighing ≥ 120 kg, all adults allocated to active tecovirimat will receive the current standard dose (as above) without adjustment for weight.

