2.9 Randomisation

Eligible individuals who have provided and consent will be allocated to tecovirimat or placebo using a minimised randomisation program that helps maximise balance between the allocated treatment groups with respect to the following prognostic variables:

- Age (<18, ≥18-<40, ≥40)
- Sex at birth (male/female)
- Previous orthopoxvirus vaccination (yes/no/not known)
- Severity of rash (localised vs disseminated, defined as >1 body area affected)
- Days since onset of rash (≤7 days or >7 days)

The implementation of the randomisation procedure will be monitored by the Senior Trials Programmer, and the Trial Steering Committee notified if an error in the randomisation process is identified.

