4.1 Outcomes

4.1.1 *Primary outcome*

The primary outcome is defined as the first day on which all skin lesions are scabbed or desquamated and mucosal lesions healed, up to 28 days after randomisation (regardless of whether active, unscabbed, lesions are reported on subsequent days). Missing values for a particular day will be imputed as the reported value taken nearest in time before or afterwards (counted in whole days; in the event of a tie the reported value taken beforehand will be used).

For time-to-event analyses of this outcome, the tecovirimat group will be compared with the placebo group using a stratified log-rank test (days since symptom onset ≤ 7 and >7 days). Kaplan-Meier estimates for the time to event will also be plotted, with associated log-rank p-values. The log-rank 'observed minus expected' statistic (and its variance) will also be used to estimate the average event rate ratio (and its confidence interval) for those allocated to tecovirimat vs placebo.

4.1.2 *Secondary outcomes*

Secondary outcome (i) is defined as the first day on which all skin lesions are completely resolved, meaning all scabs have dropped off with intact skin remaining underneath, and mucosal lesions have healed, up to 28 days after randomisation (regardless of whether unhealed lesions are reported on subsequent days). Imputation of missing data and the method of time-to-event analysis will be as for the primary outcome above.

The remaining secondary outcomes are defined as the time to consistently negative culture for monkeypox virus in serial self-collected swabs, either taken from the throat (secondary outcome (ii)), or the most recent active skin or mucosal lesion (secondary outcome (iii)). These swabs are collected on days 7, 14, 21, and 28 after randomisation, and will be analysed using an interval censored Weibull model. A negative culture will be considered 'consistently negative' if it is not followed by a positive culture on the same type of swab during subsequent assessments.

4.1.3 *Subsidiary outcomes*

Clinical status on an ordinal scale will be compared between tecovirimat and placebo groups using a proportional odds model.⁶ Howard's method will be used if the proportional odds assumption is not satisfied.⁷ Monkeypox virus DNA concentration will be compared between groups using the Wilcoxon rank-sum test.

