Time to sustained absence of use of analgesia for monkeypox symptoms is defined as the first day from which analgesia is consistently not required until day 28. Imputation of missing data and the method of time-to-event analysis will be as for the primary outcome above.

4.1.4 *Safety outcomes*

The number and percentage of patients suffering suspected serious adverse reactions, suspected unexpected serious adverse reactions, and death (overall and by cause), will be listed by trial allocation. Adverse events of special interest (listed in 2.6.4) and reasons for study drug discontinuation, will be presented by randomised group as counts and percentages. Where possible, the absolute risk differences will be presented with confidence intervals, analysed using Fisher's exact test.

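### The Weibull model for the two confirmatory culture endpoints names no baseline terms; if rash timing and severity predict culture clearance, it gives up power that could be kept at little cost

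*SAP*

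**What the plan says.** **Culture endpoints.** SAP 4.1.2 describes the swab schedule ("These swabs are collected on days 7, 14, 21, and 28 after randomisation") and says that the times to negative culture "will be analysed using an interval censored Weibull model". Protocol 2.5.1 says the same. Neither names a covariate, a stratum, an effect measure or a test, and no general statement on covariate adjustment appears elsewhere.

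**Other time-to-event outcomes.** The primary outcome uses a "stratified log-rank test (days since symptom onset ≤ 7 and >7 days") in SAP 4.1.1. For complete lesion resolution (SAP 4.1.2) and for analgesia (SAP 4.1.3), "the method of time-to-event analysis will be as for the primary outcome above". That carry-over is not made for the culture endpoints.

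**Allocation.** SAP 2.9 uses a minimisation program that "helps maximise balance between the allocated treatment groups with respect to the following prognostic variables". Two of the five factors are "Days since onset of rash (≤7 days or >7 days") and "Severity of rash (localised vs disseminated, defined as >1 body area affected"). Protocol 2.3 introduces the same five as "important prognostic variables".

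**Status.** The culture endpoints are two of the three confirmatory secondary outcomes. They are tested at two-sided 0.0476 with Benjamini-Hochberg, and only after the primary null hypothesis is rejected (SAP 4.3, protocol 2.5.1).

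**The concern.** Three time-to-event outcomes take time since onset into account and two do not, and no reason is given. A Weibull model accepts covariates directly, and the two factors are already recorded for minimisation.

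Leaving prognostic factors out of a proportional hazards model has two consequences. The treatment coefficient moves towards zero relative to the within-stratum effect, and power falls. When allocation has also been balanced on those factors, there is a third. The true sampling variance of the unadjusted estimate falls, but the model-based standard error does not follow it, so the test rejects less often than its nominal level.

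At stake is the ability to detect an effect on clearance of infectious virus, which is a stated aim (protocol 2.1) and a secondary objective (SAP 2.2). There is also a pre-specification gap. If adjustment is intended, the terms for two confirmatory tests have not been fixed.

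**Working it through.** **1. The plan's own figure.** The documents give no power for the culture endpoints. The primary endpoint calculation reproduces with Schoenfeld's formula:

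events = 4(z₀.₉₇₅ + z₀.₈₅)² / (ln 1.40)² = 4(1.960 + 1.036)² / 0.3365² = 317.2, rounded up to 318; and 318/0.77 = 413 patients.

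Its rate ratio (1.40) and event proportion (77%) are borrowed below as assumptions for culture.

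**2. Models compared.** Survival to clearance is S(t) = exp{−(t/σ)^k · exp(βA + γ₁x₁ + γ₂x₂)}, where A is treatment, x₁ timing and x₂ severity. A participant clearing between swabs L and R contributes S(L) − S(R), with limits at days 7, 14, 21 and 28. The treatment-only model sets γ₁ = γ₂ = 0. The adjusted model estimates them. The test is a Wald test at two-sided 0.0476 (|Z| > 1.981).

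**3. Main simulation.**
- From the documents: 500 × 0.9 = 450 analysed, 1:1 allocation, and the swab days.
- Assumed: 77% cleared by day 28 on placebo, shape 1.2, within-stratum rate ratio 1.40, each factor split 50/50, minimisation on both factors with a biased coin of 0.8.
- 5,000 to 8,000 trials per row.

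| Fold effect on clearance rate (timing, severity) | Null rejection, treatment-only | Mean rate ratio, treatment-only | Power, treatment-only | Power, adjusted | Loss (points) |
|---|---|---|---|---|---|
| 1, 1 | 5.1% | 1.40 | 88.3% | 88.2% | 0 |
| 1.25, 1.25 | 4.5% | 1.39 | 88.7% | 89.4% | 0.7 |
| 1.5, 1.5 | 4.1% | 1.38 | 86.9% | 89.5% | 2.6 |
| 2, 1 | 4.2% | 1.37 | 84.8% | 89.1% | 4.3 |
| 2, 2 | 3.5% | 1.34 | 80.1% | 88.2% | 8.1 |
| 3, 3 | 2.2% | 1.29 | 68.8% | 87.2% | 18.4 |

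The adjusted model gives a mean rate ratio of about 1.40 in every row and rejects in 4.7% to 5.5% of null trials. The Monte Carlo standard error with 5,000 trials is √(0.80 × 0.20/5000) = 0.6 points for power and √(0.035 × 0.965/5000) = 0.3 points for null rejection.

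**4. Hand check of the (2, 2) row**, from the simulated mean model SE and the empirical SE:
- Treatment-only power: Φ[(ln 1.3415 − 1.981 × 0.1056)/0.0995] = Φ[(0.2938 − 0.2092)/0.0995] = Φ(0.850) = 80.2%.
- Adjusted power: Φ[(ln 1.4009 − 1.981 × 0.1067)/0.1088] = Φ[(0.3371 − 0.2114)/0.1088] = Φ(1.156) = 87.6%.
- Treatment-only null rejection: 2[1 − Φ(1.981 × 0.1080/0.1006)] = 2[1 − Φ(2.127)] = 3.3%.

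The last line shows where the conservatism comes from: the model SE is 0.108 and the true SE 0.101.

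**5. Second simulation, different settings.** With 413 participants, shape 1.3 and allocation balanced within timing × severity (1,200 power runs, Monte Carlo SE about 1.2 points), power without and with the two terms was:
- two 1.5-fold factors: 81.7% and 84.4% (2.7 points);
- timing only, 2-fold: 81.2% and 84.8% (3.6 points);
- two 2-fold factors: 76.7% and 84.0% (7.3 points), with null rejection 3.3% for treatment-only (1,500 null runs).

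**6. What minimisation contributes.** Under simple randomisation with two 2-fold factors, treatment-only null rejection is 4.9%, close to nominal. The mean rate ratio is still 1.35, and power is still 79.5% against 88.4% adjusted. So only the conservatism comes from balanced allocation. The smaller ratio and the power loss come from omitting the terms.

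**7. Other clearance rates.** With two 2-fold factors the loss is 74.4 − 68.2 = 6.2 points at 50% clearance and 91.4 − 82.7 = 8.7 points at 95%. One extreme null setting (50% clearance, two 3-fold factors) gave an unstable adjusted fit with 9.8% rejection, so its adjusted result is not used.

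**The case against.** The strongest reply is that the plan is silent on covariates and does not exclude them. That is fair. A reader might infer a deliberate decision to leave them out, and the text does not show one. But as written the model contains treatment only, and if more was meant, it is not pre-specified. Either way the terms need stating.

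Other points on that side stand and limit the claim:
- The documents call the factors prognostic but do not say so for culture, and give no strengths. A certain loss of power cannot be inferred.
- The unadjusted ratio is a valid marginal quantity. It is closer to 1 than the conditional ratio, and calling it biased would presuppose a conditional estimand that the plan does not state.
- Protocol 2.2 expects antiviral effects to be greater early in disease. A reader might take this as evidence that timing predicts clearance. It concerns effect modification, and the simulations assume a constant effect across strata.
- The log-rank stratum for the primary outcome is symptom onset, whereas minimisation uses rash or lesion onset, and protocol 3.3 records fever and lesion onset separately. Consistency with those tests would support a timing term only. Severity rests on the minimisation argument.
- The power figures are for one endpoint at 0.0476. They ignore the gate on the primary and Benjamini-Hochberg, so they are not the power of the full confirmatory procedure.

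**Conclusion.** The point holds as a conditional loss of efficiency on two confirmatory secondary endpoints. A reader might go further and infer an invalid test. The results do not support that: treatment-only null rejection was at or below about 5% in every setting with prognostic factors, and it fell as they strengthened.

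The size depends on quantities that the documents do not give: prognostic strength, factor prevalence, culture clearance and the effect on culture. Under the assumptions above, the loss is negligible at 1.25-fold per factor and modest (about 3 to 4 points) for two 1.5-fold factors or timing alone at 2-fold. It becomes material (7 to 8 points, type I error about 3.5%) for two 2-fold factors. If neither factor is prognostic, the two models perform alike. Part of the gain arises because the adjusted test works at about its nominal level while the treatment-only test works below it.

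**What to change.** In SAP 4.1.2 and protocol 2.5.1, state that the interval-censored Weibull model for secondary outcomes (ii) and (iii) includes treatment, days since lesion (rash) onset at randomisation (≤7, >7 days) and rash severity (localised, disseminated). Fix these terms in advance, and report the adjusted rate ratio with its confidence interval. Take timing from the lesion-onset date used for minimisation, and note that the symptom-onset wording of the log-rank tests differs from it.

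Age, sex and vaccination status, and the proportional odds model for clinical status, are left out of this recommendation because no calculation here supports extending it to them. A rule that adds terms according to the numbers observed would reintroduce a data-dependent choice.

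The cost is a sentence in each document and two model terms from data already collected. The downside is that the reported ratio becomes conditional on timing and severity, which the report should say.

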9.2 Appendix 2: Schedule of events

	B	D1	D2	D3	D4	D5	D6	D7	D8	D9	D10	D11	D12	D13	D14	D15-20	D21	D22-27	D28
Consent	X																		
Demographics	X																		
Comorbidities	X																		
Concomitant medicines	X																		
Clinical review (remote)*	X							X							X		X		X
Patient self-assessment		X	X	X	X	X	X	X	X	X	X	X	X	X	X	X	X	X	X
Treatment administration		X	X	X	X	X	X	X	X	X	X	X	X	X	X				
Lesion swab ⁺	X [§]							X							X		X		X
Throat swab	X [§]							X							X		X		X

* Clinical review will be conducted remotely (telephone call/video call) by study clinicians or study nurses
 
⁺ Swab most recent active skin or mucosal lesion
 
[§] Diagnostic samples taken prior to baseline assessment
																			

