2.2 Objectives of the trial

The primary objective is to provide a reliable estimate of the effect of tecovirimat on the time to resolution of monkeypox skin and mucosal lesions. Secondary objectives are to estimate the effect of tecovirimat on the time to clearance of infectious monkeypox virus, and on the time to improvement in pain related to monkeypox.

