2.4 Eligibility

2.4.1 Inclusion criteria

Patients are *eligible* for the study if **all** of the following are true:

- (i) Laboratory-confirmed monkeypox infection
- (ii) The presence of active skin or mucosal lesion(s)^a
- (iii) Patient is appropriate to be managed without hospitalisation
- (iv) For women with reproductive potential,^b willingness to use effective contraception^c from the time of enrolment through study day 28

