2.6 Outcomes

2.6.1 *Primary outcome*

Time (in days) to active lesion resolution, defined as the first day on which all skin lesions are scabbed or desquamated (and mucosal lesions healed), up to 28 days after randomisation.

2.6.2 *Secondary clinical outcomes*

- (i) Time (in days) to complete lesion resolution, defined as the first day on which all lesions are completely resolved (all scabs dropped off and intact skin remains underneath, and mucosal lesions healed), up to 28 days after randomisation
- (ii) Time to negative throat swab viral culture, defined as time to consistently negative culture for monkeypox virus on throat swab at Days 7, 14, 21, and 28
- (iii) Time to negative skin or mucosa swab viral culture, defined as time to consistently negative culture for monkeypox virus on swab of most recent active skin or mucosa lesion at Days 7, 14, 21, and 28

2.6.3 *Subsidiary clinical outcomes*

- (i) Clinical status on day 7, 14, 21 and 28 according to the following ordinal scale:
 - a. All lesions completely resolved (all scabs dropped off and intact skin remains underneath, and all mucosal lesions healed)
 - b. Active lesions resolved (all skin lesions scabbed or desquamated, but not all completely resolved)
 - c. Active lesions persist but no new lesions in last 24 hours
 - d. New active lesion(s) in last 24 hours.
- (ii) Throat swab monkeypox DNA levels: monkeypox virus DNA concentration in throat swabs at Days 7, 14, 21, 28
- (iii) Number (%) of patients admitted to hospital for a complication of monkeypox (overall and by type)
- (iv) Time to sustained absence of use of analgesia for monkeypox symptoms, defined as time to consistently reporting no use of analgesia, up to 28 days after randomisation.

2.6.4 *Safety assessments*

- (i) Number (%) of patients suffering serious adverse events (overall and by type) within 28 days of randomisation
- (ii) Number (%) of patients suffering adverse events of special interest (overall and by type) within 28 days of randomisation. These are:
 - Vomiting
 - Diarrhoea
 - Fever
 - Severe tiredness
 - Swollen lymph glands
 - Headache

- Muscle or joint pain
 - Sore eyes
 - Shortness of breath
 - Secondary skin infection
 - Pain related to monkeypox symptoms
- (iii) Number (%) of patients suffering death, overall and by cause
- (iv) Reasons for prematurely stopping allocated study treatment

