2.14 Analysis population

The intention to treat (ITT) population will be all participants randomised, irrespective of treatment received. This ITT population will be used for analysis of efficacy and safety data. For interim analyses, baseline data will be reported for all participants with data available and outcome data will be reported for all participants who have reached day 28 after randomisation.

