3.2 Baseline comparability of randomised groups

The following baseline characteristics will be described separately for patients randomised to tecovirimat and placebo.

- Age at randomisation
- Sex at birth
- Time since onset of skin or mucosal lesions
- Number of active lesions (1-5, 6-25, 26-100, >100)
- Number with disseminated infection (defined as >1 body region affected)
- Proportion requiring painkillers for monkeypox
- Comorbidities (diabetes, HIV, and immunosuppression related to medication or haematological disease)
- Previous orthopoxvirus vaccination

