4 COMPARATIVE ANALYSES

For all outcomes, pairwise comparisons will be made between the tecovirimat and placebo arms performed on the ITT population at 28 days after randomisation.

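### Time to sustained absence of analgesia is analysed in all randomised participants, so those who never need analgesia are day-1 events in both arms, which shrinks the rate ratio and costs power

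*SAP*

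**What the plan says.** SAP section 4 sets one analysis set for everything: "For all outcomes, pairwise comparisons will be made between the tecovirimat and placebo arms performed on the ITT population". SAP 2.14 defines it: "The intention to treat (ITT) population will be all participants randomised, irrespective of treatment received".

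SAP 4.1.3 defines the analgesia outcome as time to sustained absence of use, "defined as the first day from which analgesia is consistently not required until day 28", with missing data and the log-rank analysis handled as for the primary outcome. Nothing in the definition refers to use at baseline. SAP 2.4.1 requires an active skin or mucosal lesion at entry, but not pain or analgesia. SAP 3.2 nevertheless lists "Proportion requiring painkillers for monkeypox" among the baseline characteristics, so the plan expects some participants who use none.

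SAP 2.2 gives a secondary objective concerning pain ("and on the time to improvement in pain related to monkeypox"), while SAP 2.6.3 classes the analgesia outcome as subsidiary.

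The throat-culture outcome is built in a similar way: "defined as time to consistently negative culture for monkeypox virus on throat swab at Days 7, 14, 21, and 28". Under SAP 4.1.2 a negative culture counts if no later swab of the same type is positive. A participant who is never throat-positive therefore enters the interval-censored Weibull model as cleared by the day 7 swab. The schedule in Protocol Appendix 2 marks the baseline swabs as "Diagnostic samples taken prior to baseline assessment".

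**The concern.** Everyone has an active lesion at entry, so everyone has something to resolve for the primary outcome. That is not so for analgesia. A participant who takes none at randomisation and none afterwards meets the definition on day 1 whatever the allocation. These events carry no information on the drug, but they enter the log-rank variance and pull the estimate toward no effect.

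This is the plan's time-to-event measure for its pain objective, and Protocol 2.4.3 calls pain relief important to patients. A null result could mean that tecovirimat does not shorten analgesia use, or that many participants had no use to shorten. The planned analysis cannot separate the two.

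**Working it through.** **The plan's own figure.** SAP 2.8 gives 318 events and 413 patients for rate ratio 1.40, 85% power, two-sided 0.05. Schoenfeld: 4(1.960 + 1.036)² / (ln 1.4)² = 317.2, rounded up to 318; 318 / 0.77 = 413. Both reproduce. The documents give no power for the analgesia or throat outcomes.

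**Inputs.**
- From SAP 2.8: N = 500 less about 10% loss = 450 evaluable; rate ratio 1.40; 77% pooled events; two-sided 0.05. The last three belong to the primary outcome and are stand-ins here.
- From SAP 2.3: 1:1 allocation, 28 days of follow-up.
- Assumed: the share f who use no analgesia at baseline and never start, varied because the documents give no figure.

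**Model.** Times in users are exponential and rounded up to whole days. The control hazard λ solves 1 − ½(e^(−28λ) + e^(−28×1.4λ)) = 0.77, so λ = 0.0447 per day. Never-users have an event on day 1. The test is the daily log-rank, unstratified, with RR = exp((O − E)/V).

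**Hand check at f = 40%** (180 never-users, 270 users):
- Users: 270 × 0.77 = 208 events, so V ≈ 208/4 = 52 and O − E ≈ 52 × ln 1.4 = 17.5.
- Users' day-1 probabilities: 1 − e^(−0.0447) = 0.0437 on control, 1 − e^(−0.0625) = 0.0606 on tecovirimat. Day-1 events in users: 135 × 0.0437 + 135 × 0.0606 = 14.1.
- Day-1 variance with everyone: k = 180 + 14.1 = 194.1, V = 194.1 × ¼ × (450 − 194.1)/449 = 27.7. Users alone: 14.1 × ¼ × (270 − 14.1)/269 = 3.4. Never-users add 27.7 − 3.4 = 24.3 to V and nothing, on average, to O − E.
- All randomised: RR = exp(17.5/76.3) = 1.26; Z = 17.5/√76.3 = 2.00; power ≈ Φ(2.00 − 1.96) = 52%.
- Baseline users: RR = exp(17.5/52) = 1.40; Z = 17.5/√52 = 2.43; power ≈ Φ(2.43 − 1.96) = 68%.

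**Simulation.**

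| Never-users f | RR, all randomised | Power | RR, baseline users | Power |
|---|---|---|---|---|
| 0% | 1.42 | 88% | 1.42 | 88% |
| 20% | 1.32 | 70% | 1.42 | 81% |
| 40% | 1.26 | 51% | 1.42 | 69% |
| 60% | 1.23 | 32% | 1.42 | 50% |

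Repeat runs agreed within about 3 percentage points of power. Users' RR sits slightly above 1.40 because daily grouping makes (O − E)/V behave like a discrete-time log odds ratio: (e^0.0625 − 1)/(e^0.0447 − 1) = 1.41. With no true effect, the all-randomised test rejected in 4.6% to 5.4% of runs.

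**Stratifying instead.** With baseline use as a log-rank stratum and everyone retained, power equalled that of the restricted analysis. In a stratum where all have the event on day 1, n − k = 0, so V = 0 and O = E, and the stratum drops out.

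**Throat culture.** Interval-censored Weibull, swabs at days 7, 14, 21 and 28, N = 450, true hazard ratio 1.40, assumed control half-time 7 or 10 days:

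| Never-positive | HR, all randomised | Power | Power, baseline positives, if all have a result |
|---|---|---|---|
| 20% | 1.32–1.33 | 79–82% | 85–87% |
| 40% | 1.25–1.26 | 60–63% | 72–75% |
| 60% | 1.19–1.20 | 39–41% | 53–54% |

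The HR in baseline positives is 1.39–1.41. The power gain depends on having baseline results. At 40%, powers of about 61% and 73% correspond to information of (0.28 + 1.96)² = 5.0 and (0.61 + 1.96)² = 6.6. As 5.0/6.6 = 0.76, the gain is gone once about 24% lack a result. The same calculation gives about 14% at 20% never-positive and 30% at 60%.

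**The case against.** The all-randomised contrast is a legitimate intention-to-treat effect, it is valid under the null, and the analgesia outcome is subsidiary and outside the confirmatory family. SAP 2.6.5 already allows exploratory analyses in baseline subsets. All of this stands, and it keeps the point to an improvement in sensitivity and interpretation. An unspecified exploratory option is still weaker than a named analysis.

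A reader might infer that every baseline non-user is an immediate success. The definition does not support that: absence must last until day 28, so someone who starts analgesia on day 5 is not a day-1 event. Participants randomised early may still be worsening, and the full analysis keeps any preventive effect in them. The table counts only those who never start, so it overstates the loss if f is read as the baseline non-user share. Protocol 2.4.3 also describes pain as very common, which favours the low end of the range.

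A reader might also infer that throat culture should be restricted to baseline positives as its main analysis. The documents do not support that. Protocol 1.3 has diagnosis resting on lesion and/or throat swabs (Protocol 3.1 says both). Protocol 3.6.1 keeps residual diagnostic material only if available. Diagnosis is by PCR while the endpoint is culture, so some PCR-positive participants may have no culturable virus to clear. With enough missing baseline results, the restriction loses power.

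**Conclusion.** The point holds for the analgesia outcome as a loss of sensitivity. With 20% to 60% never-users, the estimate falls from about 1.42 to between 1.32 and 1.23, and power is about 11 to 18 points lower than in baseline users (81 − 70 = 11; 69 − 51 = 18; 50 − 32 = 18). Restriction removes the attenuation but recovers only part of the power, because fewer informative participants remain.

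The sizes rest on assumed shares, on the primary outcome's event proportion and rate ratio as stand-ins, and on an unstratified test. The direction does not depend on these choices. A reader might infer a risk of false positives; there is none, since type I error stays near 5%.

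For throat culture the same dilution applies to participants who are never culture-positive, but the case supports only a supportive analysis. The lesion-swab outcome is less exposed, because an active lesion is required at entry.

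**What to change.** In SAP 4.1.3, make the main analysis of time to sustained absence of analgesia the comparison among participants requiring painkillers for mpox at randomisation, as already listed in SAP 3.2. Report new analgesia use among the others as a proportion by arm. Alternatively, keep all randomised participants and add baseline painkiller use as a log-rank stratum alongside time since onset.

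In SAP 4.1.2, keep the all-randomised throat-culture analysis as confirmatory. Pre-specify a supportive analysis in participants with a virus-positive baseline throat sample, where available, and state how unknown baseline status is handled.

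The cost is SAP wording, to be settled before unblinding. Painkiller need must be recorded before allocation; the baseline list in Protocol 3.3 does not name it, so the form should be checked. The restricted analysis drops participants who start analgesia later, which the new-use proportion partly covers and the stratified option avoids.
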